5.7.1. Treatment Discontinuation for Individual Subject

Subjects may decide to stop participating in the study at any time for any reason without prejudice to their future medical care by the physician or at the institution. Wherever possible, the tests and evaluations listed for the End of Treatment visit and Safety Follow-up visit should be carried out and an effort should be made to continue follow-up.

If a subject decides to discontinue study treatment, he/she should be asked if he/she is willing to be contacted by telephone for monitoring of survival.

If a subject withdraws consent, the subject's data collected up to the date of consent withdrawal will be included in the analyses. The date, stated reason for and level of consent withdrawal should be documented. Any blood or tissue samples collected up to the date of withdrawal of consent will be analyzed, unless explicitly prohibited by the subject.

The Sponsor should be notified of all subjects' decision to discontinue study treatment and all study withdrawals through the designated e-CRFs in a timely manner.

Subjects meeting any of the following criteria must discontinue study drug treatment:

- **Subject decision to discontinue study treatment** (but request agreement to return for end of treatment assessments, safety follow-up assessments and/or survival follow-up).
- **Withdrawal of consent:** no further participation
- **Lost to follow up:** A subject will be considered as lost to follow up, if he/she did not attend a scheduled visit and for whom no news can be obtained after three documented attempts

with a minimum of 15 days between the first and the last attempt. This status must be dated at the latest as the database lock.

- **Investigator decision** in the subject's interest if an SAE occurs and is considered by the Investigator liable to threaten the health of the subject or if a serious disease occurs and necessitates the prescription of a medication incompatible with the pursuit of the study. The Sponsor should immediately be informed by phone or fax or email and a report explaining the discontinuation will be forwarded to him as soon as possible.
- **Progressive disease:** at any time (to be taken into account only for treatment discontinuation).
- **Unacceptable AE or toxicity** (related or not to the study treatment) or failure to tolerate the study treatment.

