6.5.4. Dose Modification

Subjects will be monitored for AEs. The severity of AEs will be evaluated using the NCI-CTCAE v.4.03.

If a subject develops toxicity, the dose should be modified as outlined in **Table 14** and **Table 15**, which include criteria for interruption and reduction of encorafenib, binimetinib and cetuximab. All dose modifications should be based on the worst preceding toxicity. All dosing interruptions and modifications must be recorded in the e-CRF.

If a subject permanently discontinues binimetinib due to an AE or clinically significant laboratory value, they may continue to receive encorafenib in combination with cetuximab.

Due to the lack of efficacy of binimetinib, encorafenib, or cetuximab when used as single agents in subjects with *BRAF*-mutant mCRC, subjects who cannot tolerate these agents in combination with at least one other agent, should discontinue study treatment altogether, complete the end of treatment visit and continue to be followed for survival (and disease progression, if applicable).

Cetuximab may be reduced by 2 dose levels to a minimum of 150 mg/m², due to AEs or laboratory abnormalities (**Table 8**). When a dose reduction is required because of an AE, no subsequent dose re-escalation of cetuximab will be permitted for that subject for the duration of study treatment. If after resolution of an AE, treatment is resumed at the same dose, and the same toxicity reoccurs with the same severity, any re-initiation of treatment must be at the next lower dose level irrespective of duration, with some exceptions for skin toxicity.

In addition, a subject must discontinue study treatment if, after treatment is resumed at a lower dose of cetuximab, the same toxicity reoccurs with the same or worse severity.

If a subject misses > 28 consecutive days of encorafenib or binimetinib, or > 4 consecutive cetuximab doses as the result of an AE or clinically significant laboratory abnormality, then the respective agent(s) should be discontinued.

Subjects who discontinue study treatment for a study-related AE or an abnormal laboratory value must complete the end of treatment visit and continue to be followed for survival (and disease progression).

Table 8: Dose Levels for Dose Modification

	Encorafenib (mg QD)	Binimetinib (mg BID)	Cetuximab WEEKLY (mg/m²)	Cetuximab BI-WEEKLY (mg/m²) Starting from C8D1 week 29 Or at any cycle since implementation of the Urgent Safety Measure on 26 Mar 2020

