Uncomplicated Grade 1-2	Maintain dose of encorafenib. Consider temporary interruption of binimetinib until resolved to Grade ≤ 1. Then resume treatment at current dose level of binimetinib.
Complicated Grade 1-2	Consider temporary interruption of encorafenib until resolved to Grade ≤ 1. Then resume treatment at current dose level of encorafenib Interrupt dosing of binimetinib until resolved to Grade ≤ 1. Then resume treatment at 1 reduced dose level ^b of binimetinib.
Grade 3-4	Interrupt dosing of encorafenib and binimetinib until resolved to Grade ≤ 1. Then resume treatment at current dose level of encorafenib if, in the judgment of the Investigator, the toxicity is considered to be unrelated to encorafenib, or at one reduced dose level ^b . Resume treatment at 1 reduced dose level ^b of binimetinib.
Nausea/Vomiting	
Grade 1-2	Maintain dose level of encorafenib and binimetinib. Promptly institute antiemetic measure.
Grade 3	Interrupt dosing of encorafenib and binimetinib until resolved to Grade ≤ 1. Then resume treatment at 1 reduced dose level ^b of encorafenib. Resume treatment with binimetinib at the current dose if, in the judgment of the Investigator, the toxicity is considered to be unrelated to binimetinib, or at 1 reduced dose level ^b . Note: Interrupt dosing of encorafenib and binimetinib for ≥ Grade 3 vomiting or Grade 3 nausea only if the vomiting or nausea cannot be controlled with optimal antiemetics (as per local practice).
Grade 4	Permanently discontinue encorafenib and binimetinib ^f .
Interstitial lung disease/pneumonitis - Section 17.7	
Grade 1	Maintain dose level of encorafenib and binimetinib. Monitor weekly.
Grade 2	Maintain dose of encorafenib. Withhold binimetinib for up to 3 weeks. If improved to Grade 0 or 1, resume treatment at 1 reduced dose level of binimetinib. If not resolved within 3 weeks, permanently discontinue binimetinib.
Grade 3-4	Permanently discontinue binimetinib.
All Other Adverse Events (Suspected To Be Related To Encorafenib and/or Binimetinib)	
Grade 1-2	If the event is a persistent Grade 2 AE not responsive to a specific therapy, consider interruption or reduction of encorafenib and binimetinib, as applicable
Grade 3	Interrupt dosing of encorafenib and binimetinib until resolved to Grade ≤ 1 or to pretreatment/baseline level. If the event resolves ≤ 21 days, then study drug may be resumed at 1 reduced dose level ^b based upon the Investigator's discretion.

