Grade 4	Permanently discontinue encorafenib and binimetinib ^f

a : Not according to NCI-CTCAE

b : Dose reduction below 150 mg QD for encorafenib, and below 15 mg BID for binimetinib is not allowed.

c : Ophthalmic monitoring mandated for retinal events, posterior uveitis, RVO: further evaluation with specialized retinal imaging (e.g. ocular coherence tomography, fluorescein angiography). Any diagnosis of retinal events must be supported by presence or absence of symptoms, visual acuity assessment and findings in OCT.

d : For subjects enrolled with liver metastases and baseline LFT elevations.

e : Disorder characterized by redness, marked discomfort, swelling, and tingling in the palms of the hands or the soles of the feet.

f : A subject with a Grade 4 AE may resume treatment at the lower dose level if the AE recovers to Grade ≤ 1 within 28 days of discontinuing drug and, if in the opinion of the Investigator and Sponsor Medical Monitor, the event is not life-threatening and the subject can be managed and monitored for recurrence of AE. Any subjects requiring a treatment interruption of duration > 28 days must discontinue study drug permanently.

g : Refers to total bilirubin.

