10.2. SERIOUS ADVERSE EVENTS

10.2.1. Definition

A serious adverse event (SAE) includes but is not necessarily restricted to any event which:

- results in death (whatever may be the cause)

Death is an outcome of an SAE and not an SAE in itself. Death should only be reported as an SAE term when no additional information is known about a fatal event. When death is an outcome, the event(s) resulting in death should be reported (e.g., “pulmonary embolism” with a fatal outcome) and assigned severity Grade 5.

- is life-threatening
- results in persistent or significant disability/incapacity
- requires the subject’s in-patient hospitalisation or prolongation of current hospitalisation*
- is a congenital anomaly or birth defect
- is serious for other reason: medical and scientific judgment should be exercised in other situations, such as important medical events that may not be immediately life-threatening or result in death or hospitalisation but may jeopardize the patient or may require intervention to prevent one of the outcomes described in the definition above. These should also usually be considered serious.

In addition, for all subjects with COVID-19 (with critical symptoms and/or hospitalization), a Serious Adverse Event should be declared.

*Note that any hospitalisation, or prolongation of hospitalisation due to the circumstances listed below will not be notified as an SAE to the Sponsor by the Investigator:

- a visit to the emergency room, or outpatient observation that does not result in admission,
- preparation for routine health assessment/procedure (e.g. routine colonoscopy),
- planned medical/surgical admission (planned prior to entry into study trial, appropriate documentation required),
- administrative or social reasons (e.g. lack of housing, economic inadequacy, care-giver respite, family circumstances).

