10.2.2. Reporting of Serious and non-serious AEs

All AEs, serious and non-serious and regardless of causality to study drug (including the exacerbation of a pre-existing condition), will be fully recorded on the appropriate e-CRF. For each AE, the Investigator must provide its duration (start and end dates or ongoing), severity (intensity), assessment of causality and seriousness and whether corrective action or therapy was required and whether action was taken with regard to study drug treatment.

Any AE that occurs after the signing of the ICF should be recorded on the AE e-CRF page regardless the relationship with the study procedure. All AEs occurring from the first dose of study drug including the 30 days after the last dose of study (30-day follow-up period) drug must be recorded on the AE e-CRF regardless of the relationship with the study drug.

If an AE occurs more than once in the same subject during the study, each occurrence must be recorded as a separate AE.

Any SAE occurring from the signing of the ICF should be reported as an SAE regardless of the relationship with the protocol procedure or with study drug.

The investigator must notify the sponsor of this event by sending within 24 hours the "SAE Form", with all the available information about the event, to the sponsor's Corporate Vigilances e-mail dedicated box :

[contact]

In case it is not possible to send the report by e-mail it can be sent by fax to:

[name]

In addition, all SAEs must be recorded into the e-CRF.

Study disease progression (including malignant disease progression with fatal outcome), if documented by the use of appropriate method (as per protocol) will be reported as progression of study disease in the e-CRF (study end-point) and should NOT be reported as an SAE unless a causal relationship to study treatment is suspected.

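### Table 14's antiemetic note for vomiting of Grade 3 or higher takes in Grade 4 and contradicts the Grade 4 row beneath it

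*Protocol*

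**What the plan says.** The nausea/vomiting block of Table 14 has three rows, for Grades 1-2, Grade 3 and Grade 4.

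- **Grade 3 row.** Both oral drugs are held until recovery to Grade 1 or lower. Encorafenib then resumes one level down, and binimetinib at the current dose or one level down, depending on the Investigator's view of relatedness. A note closes the row: "Interrupt dosing of encorafenib and binimetinib for ≥ Grade 3 vomiting or Grade 3 nausea only if the vomiting or nausea cannot be controlled" (by optimal antiemetics, judged on local practice).
- **Grade 4 row.** "Permanently discontinue encorafenib and binimetinib", with footnote f attached and no mention of antiemetics.
- **Footnote f.** This is the only way back after a Grade 4 stop: "A subject with a Grade 4 AE may resume treatment at the lower dose level if the AE recovers to Grade" 1 or lower within 28 days of stopping. The Investigator and the Sponsor Medical Monitor must also take the view that "the event is not life-threatening and the subject can be managed and monitored for recurrence of AE".

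Section 6.5.4 sets the general rule: "All dose modifications should be based on the worst preceding toxicity". Section 4.1 carries the dose-modification recommendations unchanged into the Study extension.

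**The concern.** The note sits in the Grade 3 row but names its own, wider grade range for vomiting. Read literally, it reaches into the row below and makes even an interruption conditional on antiemetics failing, where that row orders an unconditional stop.

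What is at stake is the handling of the most severe non-fatal grade. Under the Grade 4 row both oral drugs stop, and a restart needs recovery within 28 days, a lower dose, and a joint view from the Investigator and the Sponsor Medical Monitor. Under the note, controlled Grade 4 vomiting triggers no stop, so none of those steps would follow. The literal reading of the note is the less protective one.

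**Working it through.** The plan states no figure on this point, so the check is a comparison of texts followed by a bound on frequency from the protocol's own safety tables.

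**Step 1: apply each instruction to each case.**

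| Case | Note in Grade 3 row | Grade 4 row | Agree? |
|---|---|---|---|
| Grade 3 vomiting or nausea, controlled | No interruption | Does not apply | No conflict |
| Grade 3 vomiting or nausea, not controlled | Interrupt | Does not apply | No conflict |
| Grade 4 vomiting, controlled | No interruption | Permanent discontinuation | Direct conflict |
| Grade 4 vomiting, not controlled | Interrupt | Permanent discontinuation, restart only by footnote f | Conflict, softened by footnote f |

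The conflict is confined to Grade 4 vomiting and is sharpest when antiemetics work. Nausea is not affected, because the note limits it to Grade 3.

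**Step 2: does another provision settle it?**

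- Footnote f does not. It starts from a drug that has already been stopped, whereas the note would leave the drug running.
- The worst-toxicity rule in Section 6.5.4 points a Grade 4 event to the Grade 4 row. It does not remove Grade 4 from the range stated in the note.
- The wording does not show a plain slip. The same sentence puts the sign before the vomiting grade and not before the nausea grade. Where Table 14 handles Grades 3 and 4 together (diarrhea, interstitial lung disease), the row label says so; nausea/vomiting has separate rows.

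**Step 3: how often could it arise?** The combined Grade 3/4 count is an upper bound on the Grade 4 count in each cohort.

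| Source | Regimen | Grade 3/4 vomiting | Grade 4 vomiting |
|---|---|---|---|
| Table 6 | Triplet, safety lead-in | 2/30 = 6.7% | 0 to 2 |
| Table 5 | Encorafenib 300 mg plus binimetinib, melanoma | 1/257 = 0.4% | 0 to 1 |
| Table 3 | Encorafenib 200 mg plus cetuximab | 0/50 | 0 |
| Table 4 | Binimetinib alone | 6/269 = 2.2%, all Grade 3 | 0 |

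Only Table 6 is the trial regimen, and it has 30 patients. All four tables count events regardless of causality, whereas Table 14 covers events related to encorafenib or binimetinib, so the counts can overstate what the rule reaches. None reports the share controlled by antiemetics. An expected number for this trial cannot be derived, and none is given.

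**The case against.** The strongest reply is that the table's structure already decides the matter. Table 14 is entered by worst grade, so a Grade 4 event goes to the Grade 4 row and never meets a note that qualifies the Grade 3 row. The note also limits interruption, while the Grade 4 row orders discontinuation; the protocol treats these as different actions, and a limit on one need not cancel the other.

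The conflicting case is also hard to construct. The general guideline in Section 10.1.2, given for terms that CTCAE does not list, describes Grade 4 as life-threatening, and few sites would continue oral dosing through such an event. There are backstops too. "Unacceptable AE or toxicity" is a mandatory reason to stop in Section 5.7.1. Section 10.2.1 opens its definition with "A serious adverse event (SAE) includes but is not necessarily restricted to any event which" and lists life-threatening events, and for serious events Section 10.2.2 says "The investigator must notify the sponsor of this event by sending within 24 hours the" SAE form. Finally, the sign may be deliberate, in which case deleting it chooses a reading on the sponsor's behalf.

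Much of this stands as a statement about practical risk: continued dosing through Grade 4 vomiting is unlikely, and the event is rare. It does not remove the contradiction. The note states a range that includes Grade 4, and no text gives either instruction precedence. If the sign was deliberate, the Grade 4 row is wrong for vomiting, and the two still cannot both be followed. The proposed wording keeps the more protective rule and matches the Grade 4 instruction, with the same footnote, for rash and for all other related events.

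**Conclusion.** The concern holds. For Grade 4 vomiting the note and the row beneath it give different instructions, and they are opposite when antiemetics work. The matter is minor: the wording should be corrected, but the frequency is low (at most 2 of 30 on the triplet in the protocol's own data) and several safeguards make the less protective reading unlikely in practice. It does not alter the definition of the confirmed response rate or the rule of 37 responses in 90 subjects. The conclusion rests on reading the note's grade range literally and on the absence of any precedence rule in Section 6.5.4, Table 14 or footnote f.

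**What to change.** In the note in the Grade 3 nausea/vomiting row of Table 14, remove the greater-than-or-equal sign so that the note covers Grade 3 vomiting and Grade 3 nausea only. Leave the Grade 4 row and footnote f unchanged, so that they are the only rule for Grade 4 vomiting. The Grade 3 antiemetic exception is kept.

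The cost is one deleted symbol, which can go into the next protocol amendment under Section 15.1; it does not need an amendment of its own. The benefit is limited to subjects still on treatment, since the synopsis records that the last enrolled subject started on 27 Dec 2019, but the rule continues to apply to them in the Study extension.

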6.5.4.2. Dose Modifications for Cetuximab

Recommended dose modifications for cetuximab based on the occurrence of cetuximab treatment-related AEs are summarized in **Table 15**. **Section 17.1** contains recommended guidelines for prophylactic and symptomatic treatment of cetuximab-induced rash.

Table 15: Recommended dose modifications for Cetuximab during a cycle of therapy

Worst toxicity CTCAE, v.4.03 Grade	Dose Modification for Cetuximab During a Cycle of Therapy
Infusion Reaction	If an infusion reaction occurs while cetuximab is being infused, the infusion should be stopped immediately and the subject should be evaluated.
Grade 1 or 2	Restart and complete the disrupted infusion at the discretion of the Investigator. The infusion must be restarted at a reduced rate. Additional pre-medications such as antihistamines or low-dose systemic corticosteroids may be administered when the infusion is restarted per institutional standards. All subsequent infusions must also be administered at the reduced rate.
Grade 3 or 4	Permanently discontinue cetuximab
Rash: see encorafenib and/or binimetinib dose modifications (Table 14)	
Grade 1 or 2	Maintain dose level; consider initiating appropriate therapy (such as antihistamines, topical corticosteroids, and low-dose systemic corticosteroids)
Grade 3, despite therapy	Omit dose until resolved to \leq Grade 2, then: 
 • If resolved in \leq 7 days (or \leq 14 days for acneiform rash), then maintain dose level • If not resolved in \leq 7 days despite appropriate skin toxicity therapy (or \leq 14 days for acneiform rash), then permanently discontinue cetuximab
Grade 3 recurrent	Omit dose until resolved to \leq Grade 2, then: 
 • If resolved in \leq 7 days (or \leq 14 days for acneiform rash), then decrease 1 dose level • If not resolved in \leq 7 days despite appropriate skin toxicity therapy (or \leq 14 days for acneiform rash), then permanently discontinue cetuximab • Permanently discontinue cetuximab after 3rd recurrence (i.e., upon 4th occurrence)
Grade 4, despite skin toxicity therapy	Permanently discontinue cetuximab
Interstitial lung disease - Section 17.7 : in case of ILD, for all grades, cetuximab must be discontinued	

6.6. REPLACEMENT PROCEDURE

Not Applicable

6.7. BLIND BREAKING PROCESS

Not Applicable

6.8. ACCOUNTABILITY ON SITE AND RETURN/DESTRUCTION OF INVESTIGATIONAL PRODUCT(S) AND ASSOCIATED PRODUCT(S)

The Investigator should maintain accurate written records of treatment received, dispensed, returned and any remaining treatment units, on the treatment accountability form. These records should be made available for CRA monitoring. The packaging of the medication should remain intact until just before the dispensation.

At each visit, the Investigator will record the number of capsules and tablets returned by each subject.

At the end of the study, all used and unused treatments including packaging should be noted, and will be destroyed at the center (or local warehouse if not possible at the center). A copy of the treatment accountability form should be provided by the Investigator to the CRA and a destruction certificate should be received by Sponsor.

6.9. RECALL OF INVESTIGATIONAL PRODUCT(S) AND RESCUE MEDICATION

In cases of recall of investigational products (decided by the Competent Authorities or the Sponsor), the Investigator will be immediately informed by the Sponsor.

The Investigator, in collaboration with the Sponsor representatives (Study Manager, CRA) must urgently:

- stop the delivery of the concerned investigational products to the subjects,

- inform the concerned subjects that they must immediately stop taking these investigational products and return them to the center.

The Study Manager/CRA will organize the return of the recalled products to the sponsor or designee, or will insure the destruction of the recall products at site under the investigator's responsibility (destruction certificate to be obtained).

7. CONCOMITANT THERAPY AND THERAPEUTIC / DIAGNOSTIC PROCEDURES

Any existing concomitant therapies (at screening), any new concomitant therapies or change in the dosage of an existing concomitant therapy during the course of the study must be recorded on the e-CRF (as describe in the e-CRF completion guideline). All non-essential therapies must be stopped at screening.

All medications, whether prescription or nonprescription, and non-drug therapies (e.g., blood transfusions) taken within 4 weeks prior to the first administration of study treatment, and all concomitant therapy administered during the study must be recorded on the Prior/Concomitant Therapies e-CRF page up to 30 days after the last study treatment administration.

All medications (other than study treatment) and significant non-drug therapies (including physical therapy, and blood transfusions) administered during the study must be listed on the concomitant therapies e-CRF page.

For all concomitant therapies taken during the study, the following information must be noted in the relevant section(s) of the e-CRF:

- The name of the treatment / therapy
- The reason for prescription
- The route of administration
- The dose
- The frequency
- The duration (start date and end date)

Any therapeutic and diagnostic procedures such as endoscopic examinations, diagnostics tests, ablation, surgical procedures etc. not planned by the study protocol must also be noted in the e-CRF. These procedures may be associated with events, in which case the condition that leads to the procedure must be reported in the appropriate section of the e-CRF (AEs, medical history).

For all such procedures that occur during the study, the following information must be noted in the relevant section(s) of the e-CRF:

- The name of the procedure
- The indication
- The duration (start date and end date)

